### **3.7 Efficacy**

Efficacy analyses will be conducted using the Full Analysis Set. Overall response will additionally be presented for the Response-Evaluable Set in Part 3.

The efficacy analyses for this study will be summarized by:

- Initial assigned dose levels or initial assigned dosing schedules (in the case of Part 4 biweekly) for Part 1 and Part 4 (Dose Escalation cohorts)
- Indication within monotherapy and by combination therapy for Part 2 and Part 3

#### **3.7.1 Overall Response Rate**

For each subject, a disease-specific overall assessment will be made by the investigator. The table below indicates the responder and non-responder CRF categories for each type of malignancy.

Type of Hematologic Malignancy	CRF	CRF variable label	CRF Assessment Categories (* indicates responder category, ** indicates progressive disease category)
Lymphoma (Hodgkin or Non-Hodgkin)	Response Assessment – Cheson Lugano Classification 2014	"Overall Visit Response at This Assessment"	CR*, PR*, SD, PD**, NE

Multiple Myeloma	Response Assessment – IMWG	"Overall Objective Response at this assessment"	CR*, sCR*, VGPR*, PR*, SD, PD**, Clinical Relapse**, NE, NA
Acute Myeloid Leukemia	AML Response Assessment – Cheson 2003	"Overall Objective Response at This Assessment"	Morphologic leukemia-free state*, Morphologic complete remission*, Cytogenetic complete remission*, Molecular complete remission*, Partial Remission*, Treatment Failure, Unknown
Chronic Lymphocytic Leukemia	Response Assessment – Hallek 2008	"Overall Visit Response at This Assessment"	Complete Response or Complete Remission*, Complete Response or Complete Remission with Incomplete Marrow Recovery*, Partial Response*, Relapse or Progressive Disease**, Stable Disease, Unknown
Myelodysplastic Syndrome (RAEB-1 or RAEB-2)	Response Assessment – MDS	"Overall Objective Response at this assessment"	CR: Marrow*, CR*, PR*, SD, PD**, NE, NA

A subject will be considered to be a responder if the subject had at least two consecutive assessments at which the subject is identified as a responder according to the table above. A subject will be considered to have progressive disease if the subject had at least one assessment at which the subject is identified as having progressive disease according to the table above. The earliest of the consecutive dates at which a responder assessment is made will be the Date of Response. The earliest date at which a progressive disease assessment is made will be the Date of Progression.

In the full analysis set and the response evaluable set, the Overall Response Rate (ORR) is defined as follows.

$$ORR = 100 * \frac{\text{Number of responders}}{\text{Total number of subjects}}$$

(Note that subjects having a response of NE, NA, Unknown, or missing are included in the denominator in this calculation and summarized as non-responders.)

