#### *Response Criteria*

Tumor response assessment for lymphomas (including PTCL) in both the escalation and expansion phases will utilize the Lugano Classification (Cheson et al., 2014), including the 2016 refinement of these criteria (Cheson et al., 2016). A response will be defined as an objective status of partial remission (PR) or complete remission (CR) for subjects evaluated by computed tomography (CT)-based criteria and complete metabolic response (CMR) or partial metabolic response (PMR) for subjects evaluated by positron emission tomography -CT based criteria. For CTCL, a response will be defined as PR or CR in any of the organ systems individually (skin, viscera, blood or lymph nodes). Additionally, a global response incorporating each organ system will be compiled per the Olsen criteria (Olsen et al., 2011). Radiographic disease assessments for CTCL and PTCL will be submitted for central review for those subjects enrolled to phase 1b Part 3. The subjects enrolled to phase 1b Part 4 will not require submission of scans for central review in real time but might be requested by sponsor retrospectively.

For the additional malignancies in the expansion phase, the following classification systems will be employed:

- AML and ALL – Revised Recommendations of the International Working Group for trials in AML (Cheson et al., 2003)

- CLL – International Workshop on CLL update of the NCI 1996 Guidelines (Hallek et al., 2008)
- MDS/MPN – An International Consortium Proposal of Uniform Response Criteria for Myelodysplastic/Myeloproliferative Neoplasms (MDS/MPN) in Adults (Savona et al., 2015)
- Multiple Myeloma – International Uniform Response Criteria for Multiple Myeloma (Durie et al., 2006)
- CTCL – Clinical Endpoints and Response Criteria in Mycosis Fungoides and Sezary Syndrome (Olsen et al., 2011)
- SCLC – Adaptation of the Immune-Related Response Criteria: irRECIST (Bohnsack et al., 2014)

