#### *Expansion Phase Part 3: CTCL and PTCL Cohorts*

For the phase 1b (Part 3) expansion cohorts for CTCL and PTCL, the cohort size has been selected based upon a Simon optimal 2-stage design, with the low and high boundaries of the response rate being 10% (not effective) and 30% (warrants further study) respectively, and a power of 90% and an alpha of 0.05. The calculations were performed using PASS 14 (NCSS, 2015) and the Optimum design chosen. The total sample size is 35 subjects per cohort under the scenario described below. For the first stage, a total of 18 subjects will be enrolled in each cohort. At the end of Stage 1, if 2 or fewer responders are observed per cohort, enrollment in this cohort will be terminated, otherwise, enrollment will proceed to the second stage and an additional 17 subjects will be enrolled per cohort for a total of 35 subjects per cohort. At the end of the second stage, if 6 or fewer responders are observed per cohort, the drug will be rejected for further testing in this indication. The probability of early termination (PET) = 0.734 at the end of the first stage if the true response rate is less than 10%.

N1	R1	PET	N	R	Average N	Alpha	Beta
18	2	0.734	35	6	22.53	0.047	0.098

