#### **8.4.7 CTCL and PTCL Cohorts**

##### **Phase 1b Part 3: CTCL and PTCL Cohorts**

Radiographic disease assessments for CTCL and PTCL will be centrally reviewed. Each of the 2 cohorts (CTCL and PTCL) will be evaluated separately for the potential for further study using the Simon 2-stage design. For the first stage, a total of 18 response-evaluable subjects will be reviewed in each cohort; if 2 or fewer responders are observed per cohort, enrollment in that cohort will be terminated. Otherwise, enrollment will proceed to the second stage and an additional 17 response-evaluable subjects will be enrolled per cohort for a total of 35 response-evaluable subjects per cohort. At the end of the second stage, if 6 or fewer responders are observed per cohort, the drug will be rejected for further testing in this indication. If more than the required number of response-evaluable patients are available (i.e., >18 or >35), the first 18 or 35, respectively, would be used.

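### Part 3 plans central review of scans beside the Simon rule, but no text says which read counts and the SAP specifies only the investigator's read, with no check for reader bias

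*SAP*

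**What the plan says.** **Protocol.** Section 8.4.7 opens its Part 3 paragraph with "Radiographic disease assessments for CTCL and PTCL will be centrally reviewed" and then sets out the Simon rule for the same two cohorts. Section 7.14.1 repeats the plan: "Radiographic disease assessments for CTCL and PTCL will be submitted for central review for those subjects enrolled to phase 1b Part 3". Appendix D Table 3 lists both local and central review of PET/CT for PTCL in Part 3. For CTCL in Part 3 it lists central radiographic review and both local and central blood assessment. Nowhere does the protocol rank the two reads or say which one feeds the responder count.

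Section 8.3 gives the design: "low and high boundaries of the response rate being 10% (not effective) and 30% (warrants further study) respectively", with "a power of 90% and an alpha of 0.05". On stage 1 it says "For the first stage, a total of 18 subjects will be enrolled in each cohort" and "At the end of Stage 1, if 2 or fewer responders are observed per cohort, enrollment in this cohort will be terminated". On the total it says "The total sample size is 35 subjects per cohort under the scenario described below", and the drug is rejected for the indication at 6 or fewer responders of 35.

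**SAP.** Section 1.2.4 repeats these bounds in terms of responders. The only definition of a responder is in Section 3.7.1, which begins "For each subject, a disease-specific overall assessment will be made by the investigator" and then requires two consecutive CRF assessments in a responder category. The SAP text contains no central-read response rate, no agreement table and no sensitivity analysis by reader.

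**The concern.** Part 3 is open-label and single-arm, and it carries the study's only formal efficacy rule. The investigator knows the treatment and may have an interest in keeping a subject on it. Central review is the usual protection. The protocol plans it for Part 3, while for Part 4 it drops the real-time requirement.

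If two reads exist and the plan names only one, two things are at stake. First, a consistent upward tendency in the investigator reads would raise the Part 3 response rate, and the SAP text specifies nothing that would measure it. Second, because the protocol is silent on which read decides, the choice could be made after both results are known. Each Simon bound turns on a single responder, so a small difference between readers can change the outcome.

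**Working it through.** **Inputs (Protocol 8.3, repeated in SAP 1.2.4).** Stage 1 n1 = 18, stop at r1 = 2 or fewer; total N = 35, reject at r = 6 or fewer; p0 = 0.10, p1 = 0.30. Stated values: probability of early termination (PET) 0.734, average N 22.53, alpha 0.047, beta 0.098.

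**Formulas.** With X1 ~ Bin(18, p) and X2 ~ Bin(17, p):
- PET(p) = P(X1 ≤ 2)
- average N = 18 + (1 − PET) × 17
- P(go) = Σ over x = 3 to 18 of P(X1 = x) × P(X2 ≥ 7 − x), that is, the chance of passing both bounds.

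**Reproducing the plan's figures.**
- At p = 0.10: PET = 0.1501 + 0.3002 + 0.2835 = 0.7338; average N = 18 + 0.2662 × 17 = 22.53; P(go) = 0.0474.
- At p = 0.30: P(go) = 0.9016, so beta = 0.0984.

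All four stated values match. The design calculation is not in question.

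**Effect of reader optimism (assumed).** The documents give no investigator-versus-central discordance rate. Suppose the true rate is 10% and investigator reading adds 0, 3 or 5 percentage points:

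| Investigator-read rate | P(pass stage 1) | P(go) |
|---|---|---|
| 10% | 0.266 | 0.047 |
| 13% | 0.421 | 0.141 |
| 15% | 0.520 | 0.234 |

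Alternatively, let each true non-responder be called a responder with probability f, so that the observed rate is 0.10 + 0.90f. For f = 3% this is 0.127 and P(go) = 0.129. For f = 5% it is 0.145 and P(go) = 0.209. The two ways of expressing the bias agree closely.

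**The cost in the other direction.** If the central read were made decisive and ran 3 or 5 points below a 30% investigator rate:

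| Central-read rate | P(go) |
|---|---|
| 30% | 0.902 |
| 27% | 0.828 |
| 25% | 0.759 |

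Making the central read decisive could therefore cost about 7 to 14 points of power (0.902 − 0.828 = 0.074; 0.902 − 0.759 = 0.143).

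**How much of the endpoint central review covers.**
- PTCL: response is by the Lugano criteria on imaging, and scans have both local and central review. A comparison of reads is fully meaningful.
- CTCL: Protocol 7.14.1 counts a response in any of skin, viscera, blood or nodes. Appendix D Table 3, footnote b, restricts imaging after screening to subjects with visceral lesions at screening and to confirming a response. Blood has a planned central review. Skin is scored by mSWAT and CAILS; photographs go to central storage (footnote k), but no central scoring is described. A comparison of reads covers only part of this endpoint.

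**The case against.** The strongest reply is that the SAP breaks no protocol rule. The protocol plans central review but never makes it decisive, and for PTCL it lists both reads side by side. That stands: a reader might infer that the SAP departs from a central-read Simon rule, but no such rule is written. What is missing is the choice of read and an analysis of the other one.

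A reader might also infer that investigator optimism passes directly into the decision to continue. The documents do not support that. Under the Synopsis and Protocol 3.4, the Safety Review Committee recommends and the sponsor decides on Stage 2. Durability, safety and the competitive setting may also weigh, and nothing says central reads would be withheld. SAP 1.2.6 plans no interim efficacy analysis, so the SAP's definition does not govern Stage 1. The link is firmer for the final 6-of-35 comparison, because the SAP offers only one definition of a responder.

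Nor can one say that no output would reveal a reader difference. The list of tables is a separate document (SAP 5) that was not available, and the SAP Introduction excludes analyses by the sponsor and other vendors. The statement has to be limited to the SAP text.

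Two further points temper the size. Requiring two consecutive responder assessments, and counting unevaluable subjects as non-responders, dampens isolated over-calls, though not consistent optimism by the same reader. And the documents do not say on which reader's scale the 10% and 30% boundaries were set. If it was the investigator's, the investigator count is the like-for-like one and the illustrated inflation does not follow.

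**Conclusion.** The gap is real and moderate. Central review is planned for Part 3 beside the Simon rule, no text says which read counts, and the SAP text analyses only the investigator's. As written, the Part 3 response rate and the 6-of-35 comparison rest on unblinded reads with no specified check.

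The size is unknown. The rise from 0.047 to 0.141 or 0.234 assumes a true rate of 10%, a one-directional difference of 3 or 5 points, and boundaries that refer to the true rate. It shows how sensitive the design is and does not estimate any bias in this trial. The point bears mainly on PTCL; in CTCL it reaches only imaging where done, and blood. It does not touch the primary endpoint, which is safety. Which read should be decisive is a judgement with a power cost; reporting both is worthwhile either way.

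**What to change.** In SAP 3.7.1, add for Part 3:
1. A statement of which read counts toward the Simon bounds.
2. For PTCL, the response rate by the other read, and an investigator-versus-central agreement table.
3. The Simon outcome (more than 2 of 18, more than 6 of 35) under both reads.
4. For CTCL, the same comparison limited to the centrally reviewed components (nodal and visceral imaging where done, and blood), with a note that no central read of skin scoring is described. The response table in this section also has no row for the CTCL global response criteria; adding one would make clear what is being compared.

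The cost is SAP wording and two more tables, using reviews the protocol already plans. The central-read rate may be lower or disagree with the investigator's, and the report would then have to discuss it. If the sponsor makes the central read decisive, it should accept the possible power loss shown in the working (0.90 to 0.83 or 0.76). If it keeps the investigator read, items 2 and 3 still provide the check.

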#### 8.4.6 Efficacy Analyses

Efficacy analyses will be conducted using the Full Analysis Set and, where appropriate, the Per-protocol Set; in addition, the overall response rate will also be presented for the Response-Evaluable Set.

The overall response rate will be estimated for each cohort using disease-specific response criteria (see [Section 7.14.1](#)). The duration of response (DOR) will be calculated for a subject who achieves a response, and is defined as the number of weeks from the start date of the response (and subsequently confirmed) to the first date recurrent or progressive disease is documented. If a subject dies, irrespective of cause, without documentation of recurrent or progressive disease beforehand, then the date of death will be used to denote the response end date.

Progression-free survival (PFS) is defined as the number of weeks from the date of the first dose of study drug to the earliest of documented recurrent or progressive disease or death due to any cause without prior progression. Leukemia-free survival (LFS) will be calculated in the same manner, as appropriate.

DOR and PFS will be summarized descriptively using the Kaplan-Meier method with 95% CI calculated using Greenwood's formula. Median follow-up for each endpoint will be estimated according to the Kaplan-Meier estimate of potential follow-up. The PFS rate at selected landmarks (e.g., 6 months) and corresponding 95% CIs will be estimated using the Kaplan-Meier method. Greenwood's formula will be used to calculate the standard errors of the Kaplan-Meier estimate and upper and lower limits of the 95% CI.

For DOR and PFS, subjects who meet one or more of the following conditions will be right-censored as follows:

- subjects with no baseline or postbaseline disease assessments unless death occurred prior to the first planned assessment (in which case the death will be considered a PFS event)
- subjects who initiate subsequent anticancer therapy in the absence of documented progression
- subjects who die or have disease progression after missing 2 or more consecutively scheduled disease assessment visits
- subjects who are last known to be alive and progression-free on or before the data cut-off date

For such subjects, the progression or censoring date will be determined based on described conventions (Food and Drug Administration, 2007), as outlined in the SAP.

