### **3.7.2 Duration of Response and Progression Free Survival Time**

The time-to-event endpoints measured in this study are defined in terms of the following dates.

- Date of first dose = Date of first dose as recorded on Treatment CRF
- Date of response = Earliest of the consecutive dates at which subject is assessed in a responder category
- Date of last non-PD assessment = Date of last non-missing assessment other than NE, NA, or Unknown
- Date of progression = Date at which subject is first assessed as having progressive disease
- Date of initiation of anticancer treatment = Earliest concomitant medication start date for concomitant medications identified by sponsor as being anticancer treatments

- Date of death = Date of death from any cause as recorded on Death Page CRF

The following time-to-event endpoints will be calculated for each subject.

- DOR for subjects who achieved an objective response = Duration of response (in weeks) =  $[\min(\text{Date of progression}) - \text{Date of response} + 1]/7$
- PFS = Progression free survival time (in weeks) =  $[\min(\text{Date of progression}, \text{Date of death}) - \text{Date of first dose} + 1]/7$

In the case of missing dates (ie, subjects without an event), the following censoring rules will be applied.

Endpoint	Censor if:	Censoring date = Minimum of indicated dates		
		Date of last non-PD assessment	Date of initiation of anticancer treatment	Date of death
DOR	Death prior to progression			X
DOR or PFS	Subsequent anticancer therapy is initiated in the absence of documented progression		X	
	Death or progression after $\geq 2$ assessments of NE, NA, Unknown, or Missing	X		
	Alive & progression free	X	X	

DOR and PFS will be displayed in listings.

The number of subjects with event for DOR and PFS will be summarized. Median time to event, the 25th and 75th percentiles of time to event, along with 95% CI for DOR and PFS will be estimated according to the Kaplan-Meier estimate using the Brookmeyer-Crowley method.

Additionally, the PFS rate at selected landmarks (e.g., 6 months) and corresponding 95% CIs will be estimated using the Kaplan-Meier method. Greenwood's formula will be used to calculate the standard errors of the Kaplan-Meier estimate and upper and lower limits of the 95% CI.

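### SAP 3.7.2 censors duration of response at death, where the protocol ends it, and SAP 3.7.1 gives AML no category that can record progression

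*SAP*

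**What the plan says.** **Death and DOR.** Protocol 8.4.6 ends a response at the first documented recurrence or progression. It adds that if a subject dies of any cause "without documentation of recurrent or progressive disease beforehand, then the date of death will be used to denote the response end date". The efficacy paragraph of the synopsis says the same. In SAP 3.7.2 the DOR formula has the date of progression as its only end date, and the censoring table has a row for DOR alone, "Death prior to progression", which censors at the date of death. The PFS formula in the same section takes the earlier of progression and death.

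**Progression in AML.** In the SAP 3.7.1 table one asterisk marks a responder category and two mark progressive disease. A subject has progressed only if there is at least one assessment "at which the subject is identified as having progressive disease according to the table above". The AML row reads "Morphologic leukemia-free state*, Morphologic complete remission*, Cytogenetic complete remission*, Molecular complete remission*, Partial Remission*, Treatment Failure, Unknown". The CLL row names relapse together with progressive disease and gives that category the double asterisk; the myeloma row marks clinical relapse in the same way.

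**Last assessment without progression.** SAP 3.7.2 defines "Date of last non-PD assessment = Date of last non-missing assessment other than NE, NA, or Unknown". Treatment Failure is not on the excluded list.

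**The concern.** Two separate rules in the SAP remove events that the protocol counts. The first concerns all cohorts: a responder who dies without documented progression leaves the DOR analysis as if the response might still be continuing. The second concerns AML: relapse has no category that produces a progression date. Together they leave the AML DOR analysis with no possible event.

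AML is a Part 2 monotherapy cohort, and SAP 3.7 summarises efficacy by indication, so these outputs are planned. What is at stake is a flattering summary of DOR and of AML PFS in the study report. The synopsis also lists durability of response among the things that may influence whether the Part 3 cohorts proceed to Stage 2. The documents do not show that any decision was affected.

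**Working it through.** **1. The DOR end date, side by side.**
- Protocol 8.4.6: earlier of recurrence or progression and death, with right-censoring for new anticancer therapy without documented progression, and for death or progression after two or more consecutive missed scheduled assessments.
- SAP 3.7.2: DOR = [min(date of progression) − date of response + 1]/7, with death before progression censored at death.

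The formula and the censoring row agree with each other, so this is not a slip in one place. The conflict covers deaths outside the protocol's own two censoring rules.

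**2. Direction of the effect on DOR.** The Kaplan-Meier estimate is S(t) = Π(1 − dᵢ/nᵢ). For these deaths both rules stop the clock on the same date, so the risk sets nᵢ are the same. A death contributes the factor 1 − 1/nᵢ under the protocol and 1 under the SAP. With all else equal, the SAP curve is nowhere below the protocol curve.

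**3. Progression categories by row of the SAP 3.7.1 table.** Lymphoma 1, multiple myeloma 2, CLL 1, MDS 1, AML 0. The AML row has 7 categories: 5 responder categories, plus Treatment Failure and Unknown, both unmarked. SAP 3.7.2 names no other source for the date of progression, although Protocol 7.13 collects one in long-term follow-up.

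**4. Check by enumeration.** Four AML assessments give 7⁴ = 2,401 sequences; each with or without a later death makes 4,802 paths. Of these, 3,850 contain the two consecutive responder assessments that the SAP requires.
- SAP rules: 0 progressions in 4,802 paths and 0 DOR events in 3,850 responder paths.
- Death ends the response, as in the protocol: 1,925 DOR events.
- In addition, Treatment Failure after a confirmed response counts as relapse (an assumed mapping): 2,300.

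These are counts of paths, not probabilities. The censoring rules for new therapy and missed assessments are not applied.

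**5. One hypothetical AML subject.** Responder at Week 8 (Day 56) and Week 16; relapse established at Week 24 (Day 168) and recorded as Treatment Failure.
- Protocol, using the SAP's day count: DOR (168 − 56 + 1)/7 = 16.1 weeks and PFS (168 − 1 + 1)/7 = 24.0 weeks, both events.
- SAP, death on Day 210, no new therapy: DOR (210 − 56 + 1)/7 = 22.1 weeks, censored; PFS (210 − 1 + 1)/7 = 30.0 weeks, event.
- SAP, alive with no later assessment: Day 168 is the last non-PD assessment, so DOR 16.1 and PFS 24.0 weeks, both censored. The subject is treated as alive and progression-free.

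**6. Where the SAP is unclear.**
- New therapy on Day 182, death on Day 210: PFS is censored at (182 − 1 + 1)/7 = 26.0 weeks if the new-therapy row applies. It is an event at 30.0 weeks if the table covers only subjects without an event, as its lead-in says.
- Death on Day 350, nothing assessed at Weeks 36 and 48: PFS is censored at 24.0 weeks if those visits count as Missing, and an event at (350 − 1 + 1)/7 = 50.0 weeks if they do not.

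DOR is censored in both cases on either reading.

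**The case against.** **The SAP may refine the protocol.** Protocol Section 8 leaves final details of the methods to the SAP, and the SAP history says that version 2.0 also reflects notes-to-file and sponsor recommendations. That allows for a deliberate change, but none is stated. Protocol 8.4.6 leaves the SAP to set out the dates for the subjects on its right-censoring list. A death without prior progression is not on that list unless it follows new therapy or two missed assessments.

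**An asterisk may have been lost in text extraction.** This is possible but unlikely: the marks survive in the other four rows and on all five AML responder categories. The DOR conflict does not depend on it.

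**The AML effect may be nil.** This stands in part. The cohort is closed, and the AML DOR defect bites only if there is at least one confirmed responder.

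**Stronger readings that the documents do not support.**
- A reader might infer that new therapy after an AML relapse always censors PFS, through the row "Subsequent anticancer therapy is initiated in the absence of documented progression". The lead-in limits the table to subjects without an event, and death is an event in the PFS formula. New therapy is also dated from concomitant medications, which Protocol Section 7 records only through safety follow-up, while SAP 3.5.4 describes a separate CRF for subsequent therapy.
- A reader might want the share of AML PFS events lost, or the rise in the PFS rate. The open cases above, and the absence of any AML progression, survival or response figure, mean that such a number would rest on invented inputs.
- A reader might infer that CTCL response is also misclassified, because its only possible row names the Lugano form. SAP 3.7.3 presents organ-system response citing the 2011 mycosis fungoides and Sézary criteria, and Protocol 8.1.2 and 8.1.3 list that endpoint separately from overall response. No effect on CTCL results or on the Simon decision can be shown.

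**Conclusion.** The point holds in two parts.

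First, SAP 3.7.2 reverses the protocol's treatment of death in DOR for every cohort, apart from deaths that Protocol 8.4.6 itself censors. The direction is certain: with all else equal, the Kaplan-Meier DOR curve is raised or unchanged.

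Second, as SAP 3.7.1 is written, an AML subject can never have a date of progression. AML DOR therefore has no event if there is any confirmed responder, and its median cannot be estimated. AML PFS events can only be deaths, and a living subject with Treatment Failure is censored as progression-free.

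The size cannot be determined from the documents. AML responder and event counts are not given, and the order and scope of the censoring rows are unclear. The endpoints are secondary and descriptive, so the harm is a misleading efficacy summary rather than a failed test. It should be fixed before the tables are produced. The second part assumes that the table's marks are complete as shown.

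**What to change.** 1. **SAP 3.7.2.** Define DOR = [min(date of progression, date of death) − date of response + 1]/7 and delete the row that censors DOR at death. Keep the new-therapy and missed-assessment censoring of Protocol 8.4.6.
2. **SAP 3.7.1.** Add an AML relapse and progression rule so that recurrence ends response and PFS, as Protocol 8.4.6 requires. One option is to count Treatment Failure after a prior responder assessment as relapse, and to use the progression date collected under Protocol 7.13. Check the mapping against the CRF and the cited AML criteria, neither of which is in the documents. Do not count every Treatment Failure as progression: the row has no stable-disease category, so the term may also cover failure to respond.

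The cost is edits to one table, one formula and the censoring rules, plus programming and the CRF check. If the CRF has no separate relapse field, relapse has to be derived from prior response plus Treatment Failure. The downside is that DOR in all cohorts and PFS in AML may become shorter.
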